8.5.1. Extent of Exposure to CAB

Duration of exposure to CAB and cumulative dose (see Section 10.6.2 for the definition) will be summarized for the oral phase and the injection phase separately. Overall exposure to the study drug and to the study (for safety evaluation) will also be calculated and summarized. Exposure data will also be listed.

Table 15 provides an overview of the planned analyses, with full details of data displays being presented in Appendix 14: List of Data Displays.

Table 15 Overview of Planned Analyses for Extent of Exposure

Display Type	Data Displays Generated						
	Stats Analysis			Summary		Individual	
	T	F	L	T	F	F	L
Extent of Exposure							
Extent of exposure				Y			Y

NOTES:

- T = Table, F = Figure, L = Listing, Y = Yes display generated.
- Stats Analysis = Represents TFL related to any formal statistical analyses (i.e. modelling) conducted.
- Summary = Represents TFL related to any summaries (i.e. descriptive statistics) of the observed raw data.
- Individual = Represents FL related to any displays of individual subject observed raw data.

8.5.2. Possible suicidality-related Adverse Events

Possible suicidality-related will be listed.

[Table 16](#) provides an overview of the planned analyses, with full details of data displays being presented in [Appendix 14](#): List of Data Displays.

Table 16 Overview of Analyses for possible suicidality-related AEs

Display Type	Data Displays Generated						
	Stats Analysis			Summary		Individual	
	T	F	L	T	F	F	L
AE Analyses							
Possible Suicidality-Related Adverse Event							Y

NOTES:

- T = Table, F = Figure, L = Listing, Y = Yes display generated.
- Stats Analysis = Represents TFL related to any formal statistical analyses (i.e. modelling) conducted.
- Summary = Represents TFL related to any summaries (i.e. descriptive statistics) of the observed raw data.
- Individual = Represents FL related to any displays of individual subject observed raw data.

8.5.3. Social Harms

Details of social harms collected on the eCRF will be listed for each participant.

[Table 17](#) provides an overview of the planned study population analyses, with full details of data displays being presented in [Appendix 14](#): List of Data Displays.

Table 17 Overview of Planned Study Population Analyses

Display Type	Data Displays Generated		
	Table	Figure	Listing
Social Harms			
All Social Harms			Y

NOTES:

- Y = Yes display generated.

8.5.4. ECG

ECG test will be performed at Screening only. Details collected on the eCRF will be listed for each subject. Baseline ECG findings (normal, abnormal – not clinically significant, or abnormal - clinically significant) will be summarized by number and percentage of subjects and presented as part of the ‘Demographic Characteristics’ table.

Table 18 provides an overview of the planned study population analyses, with full details of data displays being presented in Appendix 14: List of Data Displays.

Table 18 Overview of Planned Study Population Analyses

Display Type	Data Displays Generated		
	Table	Figure	Listing
ECG			
ECG Parameters and Results	Y		Y

NOTES:

- Y = Yes display generated.

8.5.5. Cardiovascular Events

Any cardiovascular events will be listed only.

Table 19 provides an overview of the planned cardiovascular event analyses, with full details of data displays being presented in Appendix 14: List of Data Displays.

Table 19 Overview of Planned Cardiovascular Event Analyses

Display Type	Data Displays Generated						
	Stats Analysis			Summary		Individual	
	T	F	L	T	F	F	L
CV Event Analyses							
All CV events							Y

NOTES:

- T = Table, F = Figure, L = Listing, Y = Yes display generated.
- Stats Analysis = Represents TFL related to any formal statistical analyses (i.e. modelling) conducted.
- Summary = Represents TFL related to any summaries (i.e. descriptive statistics) of the observed raw data.
- Individual = Represents FL related to any displays of individual subject observed raw data.

8.5.6. Liver Events

Number and percentage of subjects with liver events will be tabulated by study phase. Number and percentage of subjects with clinical significant hepatobiliary laboratory abnormalities during the study will also be tabulated. Full information of liver events will be listed.

Table 20 provides an overview of the planned liver event analyses, with full details of data displays being presented in Appendix 14: List of Data Displays.

Table 20 Overview of Planned Liver Event Analyses

Display Type	Data Displays Generated						
	Stats Analysis			Summary		Individual	
	T	F	L	T	F	F	L
Liver Event Analyses							
All liver events				Y			Y
Hepatobiliary laboratory abnormalities				Y			

NOTES:

- T = Table, F = Figure, L = Listing, Y = Yes display generated.
- Stats Analysis = Represents TFL related to any formal statistical analyses (i.e. modelling) conducted.
- Summary = Represents TFL related to any summaries (i.e. descriptive statistics) of the observed raw data.
- Individual = Represents FL related to any displays of individual subject observed raw data.

10. APPENDICES

Section	Appendix
RAP Section 4 : Analysis Populations	
Section 10.1	Appendix 1 : Protocol Deviation Management and Definitions for Per Protocol Population
RAP Section 5 : General Considerations for Data Analyses & Data Handling Conventions	
Section 10.2	Appendix 2 : Time and Events
Section 10.3	Appendix 3 : Assessment Windows
Section 10.4	Appendix 4 : Treatment States & Phases
Section 10.5	Appendix 5 : Data Display Standards & Handling Conventions 
 • Study Treatment & Sub-group Display Descriptors • Baseline Definitions & Derivations • Reporting Process & Standards
Section 10.6	Appendix 6 : Derived and Transformed Data 
 • General, Study Population & Safety
Section 10.7	Appendix 7 : Premature Withdrawals & Handling of Missing Data 
 • Premature Withdrawals • Handling of Missing Data
Section 10.8	Appendix 8 : Values of Potential Clinical Importance
Section 10.9	Appendix 9 : Multicentre Studies
Section 10.10	Appendix 10 : Examination of Covariates and Subgroups & Other Strata
Section 10.11	Appendix 11 : Multiple Comparisons and Multiplicity
Section 10.12	Appendix 12 : Model Checking and Diagnostics for Statistical Analyses
Other RAP Appendices	
Section 10.13	Appendix 13 : Abbreviations & Trade Marks
Section 10.14	Appendix 14 : List of Data Displays

10.1. Appendix 1: Protocol Deviation Management and Definitions for Per Protocol Population

Protocol waivers or exemptions are not allowed with the exception of immediate safety concerns that may arise after the oral administration of CAB.

Deviations from inclusion and exclusion criteria are not allowed because they can potentially jeopardize the scientific integrity of the study, regulatory acceptability or participant safety. Therefore, adherence to the criteria as specified in the protocol is essential

10.1.1. Exclusions from Per Protocol Population

Not applicable. Per protocol population is not defined in this study.

10.2. Appendix 2: Time & Events

10.2.1. Protocol Defined Time & Events

Table 21 Schedule of Activities^a

Clinical Assessments	Screening ^a	Oral Phase ^m		Injection Phase													Follow-up Phase & Final Visit	
		Day 1	Day 28 (Week 4)	Day 35 (Week 5) Injection 1	Day 42 (Week 6)	Week 9 Injection 2	Week 10	Week 17 Injection 3	Week 18	Week 25 Injection 4	Week 26	Week 33 Injection 5	Week 34	Week 37	Week 41	Week 53, 65, 77	Week 89	
Written informed consent	X																	
Inclusion/Exclusion criteria ^b	X																	
Demographic information	X																	
Full physical exam/medical history ^c	X																	X
Brief physical exam		X	X	X	X	X	X	X	X	X	X	X	X	X	X	X		
Height/weight/BMI ^d	X																	X
Medication/drug/alcohol history	X																	
HIV counseling	X	X	X	X	X	X	X	X	X	X	X	X	X	X	X	X	X	X
Offer condoms and lubricant	X	X	X	X	X	X	X	X	X	X	X	X	X	X	X	X	X	X
Dispense oral study medication (with counseling) ^e		X																
Drug accountability (pill counts)		X	X															

Clinical Assessments	Screening ^a	Oral Phase ^m		Injection Phase												Follow-up Phase & Final Visit	
		Day 1	Day 28 (Week 4)	Day 35 (Week 5) Injection 1	Day 42 (Week 6)	Week 9 Injection 2	Week 10	Week 17 Injection 3	Week 18	Week 25 Injection 4	Week 26	Week 33 Injection 5	Week 34	Week 37	Week 41	Week 53, 65, 77	Week 89
CAB LA Injection (with counseling)				X		X		X		X		X					
HIV-PrevTSQc ^f							X										
ISR AE Diary ^g				X		X		X		X		X					
AE		X	X	X	X	X	X	X	X	X	X	X	X	X	X	X	X
SAE review (SAE will be collected from the signing of ICF)	X	X	X	X	X	X	X	X	X	X	X	X	X	X	X	X	X
Concomitant medication check		X	X	X	X	X	X	X	X	X	X	X	X	X	X	X	X
Vital signs ^h	X	X		X	X	X	X	X	X	X	X	X	X	X	X	X	X
Qualitative HIV RNA by NAAT ⁱ	X																
HIV PoC test ^j	X	X		X		X		X		X		X			X	X	X
ECG ^k	X																
HbsAg and HbsAb, HCV Antibody	X																
Hematology/Chemistry testing	X	X	X	X	X	X		X		X		X			X		X
Urinalysis	X														X		
Urine screen for Chlamydia and gonorrhea	X																
Liver Chemistry Tests ^l																X	

Clinical Assessments	Screening ^a	Oral Phase ^m		Injection Phase												Follow-up Phase & Final Visit	
		Day 1	Day 28 (Week 4)	Day 35 (Week 5) Injection 1	Day 42 (Week 6)	Week 9 Injection 2	Week 10	Week 17 Injection 3	Week 18	Week 25 Injection 4	Week 26	Week 33 Injection 5	Week 34	Week 37	Week 41	Week 53, 65, 77	Week 89
Fasting lipid profile	X															X	
Coagulation testing	X															X	
TRUST for Syphilis screen	X																
Plasma for CAB concentration ^{m,n,o}		X ^m	X	X	X	X	X	X	X	X	X	X	X	X	X	X	X
Plasma storage sample ^p	X	X	X	X	X	X	X	X	X	X	X	X	X	X	X	X	X

AE: Adverse events, BMI: Body mass index, CAB: Cabotegravir, CAB LA: Cabotegravir long-acting, ECG: Electrocardiogram, HbsAg: Hepatitis B surface antigen, HIV: Human Immunodeficiency Virus, HCV: Hepatitis C Virus, ISR: Injection site reactions, SAE: Serious adverse event, HIV-PrevTSQc: HIV-Prevention Treatment Satisfaction Questionnaire (change); TRUST: Tolidine Red Unheated Serum Test, RNA: Ribonucleic acid.

- a. Screening (including drug screen) is to be performed within 30 days of the first dose in the Oral Phase of the study. See Appendix 2 from the study protocol
- b. Inclusion/exclusion criteria will be fully assessed at the Screening visit. Changes between the screening visit and the Day 1 visit should be assessed to ensure eligibility, including additional assessments performed at Day 1.
- c. A full physical exam will be performed at Week 89.
- d. Weight will be collected at Screening and at Week 89. Height and BMI will be collected at Screening only.
- e. Oral phase consists of 28 days with a 7 day washout period between Day 28 (last oral dose) and Day 35 (first injection visit).
- f. HIV-PrevTSQc: HIV-Prevention Treatment Satisfaction Questionnaire (change) will be given at Week 10 only (after 2nd injection).
- g. ISR AE 7 Day Post Injection Diary will be distributed at the injection visit at Week 5, 9, 17, 25 and 33 and returned to the clinic at weeks 6, 10, 18, 26, and 34. For participants having ISR on the last day of week 5, 9, 17, 25 and 33, additional ISR AE Weeks 2 – 12 Post Injection Diary will be distributed at weeks 6,10, 18, and 26,34. Participants will be asked to bring the diary to each clinic visit.
- h. Vital sign measurements will be performed following 5 minutes of rest.
- i. Qualitative HIV Nucleic Acid Amplification Testing (NAAT) will be performed at Screening. See Appendix 9 from the study protocol for the HIV testing algorithm at screening, Day 1 and during the course of the study.

- j. HIV PoC (Point of care) test will be performed at each time point during the course of the study and must be reviewed prior to IM dosing. See Appendix 9 from the study protocol for the HIV testing algorithm at screening, Day 1 and during the course of the study.
- k. ECGs will be performed following 5 minutes of rest in a semi-supine position.
- l. Liver Chemistry Tests include Alanine aminotransferase (ALT), Aspartate aminotransferase (AST), Bilirubin total and direct.
- m. Oral Pharmacokinetic (PK) sampling at trough will be collected for all subjects prior to dose within 20 to 28 hours following oral administration the day prior. Intensive oral PK sampling will be collected from approximately 16 participants as shown in Table 20.
- n. PK sampling for Injection phase: All PK samples will be collected prior to CAB LA injections at Week 5, 9, 17, 25, and 33 with the exception of 1-week post injection samples at Weeks 6, 10, 18, 26, 34, 37 (2-week post injection sample) and Week 41
- o. Long-term follow up PK samples: PK sampling during follow up will occur at, Week 53, 65, 77, and 89.
- p. Additional testing is required for participants who have a reactive or positive HIV test after enrolment. Stored plasma from the visit previous to the positive test should be tested for HIV using the 4th generation HIV test to best estimate time of infection. HIV acquisition must be confirmed by either western blot, HIV 1/2 Multispot or the Geenius HIV Confirmation 1/2 Assay, and HIV RNA.
- q. Visit may occur in a window ± 3 Day

Table 22 Schedule of Intensive Oral PK (Approximately 16 Participants) ^{a,b}

	Day 25	Day 26	Day 27							Day 28	
	Check- in	Oral dose administered (e.g. 8AM)	Prior to oral dose (e.g. 7:55AM)	Oral dose administered (e.g. 8AM)	1-hour post dose (e.g. 9AM)	2-hour post dose (e.g. 10AM)	3-hour post dose (e.g. 11AM)	4-hour post dose (e.g. 12AM)	8-hour post dose (e.g. 4PM)	24-hour post dose (e.g. 8AM)	Oral dose administered (e.g. after 8 AM)
Plasma for CAB concentration			X		X	X	X	X	X	X	

- a. PK sampling may occur ± 15 min
- b. Central lab tests for the intensive oral PK subjects refer to Table 21.

10.3. Appendix 3: Assessment Windows**10.3.1. Assessment Windows**

The nominal visit information collected on CRF will be used in the analysis. Analysis visit based on the time window will not be defined in this study.

10.4. Appendix 4: Study Phase and State

10.4.1. Treatment Phases

Assessments and events will be classified according to the time of occurrence relative to the start date of study treatment.

Treatment Phase	Definition
Screening Phase	Date < Date of first Oral CAB
Oral Phase	Date of First Oral CAB <= Date <= Date of First CAB LA Injection -1 day; for subjects who discontinued before receiving CAB LA Injection, the end date of the oral phase is the date of last study visit.
Injection Phase	Date of First CAB LA Injection <= Date <= 8 weeks after Last CAB LA Injection
Follow-up Phase	Date > 8 weeks after Last CAB LA Injection

10.4.2. Treatment States

Assessments and events will be classified according to time of occurrence relative to the start date of the study treatment.

10.4.2.1. Treatment States for AE Data

Treatment State	Definition
Screening Phase	AE Start Date < Date of First Oral CAB
On-Oral CAB-Treatment	Day 1 ≤ AE Start Date ≤ Date of First CAB LA Injection – 1; for subjects who withdraw from oral CAB treatment, Day 1 ≤ AE Start Date ≤ Withdrawal date + 7 days
On-CAB LA-treatment	Date of First CAB LA Injection ≤ AE Start Date ≤ Date of Week 41 Visit ; for subjects who withdraw from CAB LA injection, Date of First CAB LA Injection ≤ AE Start Date ≤ Date of Last CAB LA Injection + 8 Weeks
Post-Treatment	AE Start Date > Date of Last CAB LA Injection + 8 weeks
Onset Time Since 1 st Dose (Days)	If Date of First Oral CAB (or CAB LA injection) >AE Onset Date, duration = AE Onset Date - Treatment Start Date If Date of First Oral CAB (or CAB LA injection) ≤ AE Onset Date, duration = AE Onset Date - Treatment Start Date +1 Missing otherwise.
AE Duration (Days)	AE Resolution Date – AE Onset Date + 1
Drug-related	If relationship is marked 'YES' on CRF OR value is missing

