- HIV PoC (Point of care) test will be performed at each time point during the course of the study and must be reviewed prior to IM dosing. See [Appendix 9](#) for the HIV testing algorithm at screening, Day 1 and during the course of the study.
- ECGs will be performed following 5 minutes of rest in a semi-supine position.
- Liver Chemistry Tests include Alanine aminotransferase (ALT), Aspartate aminotransferase (AST), Bilirubin total and direct.

- m. Oral Pharmacokinetic (PK) sampling at trough will be collected for all subjects prior to dose within 20 to 28 hours following oral administration the day prior. Intensive oral PK sampling will be collected from approximately 16 participants as shown in [Table 2](#).
- n. PK sampling for Injection phase: All PK samples will be collected prior to CAB LA injections at Week 5, 9, 17, 25, and 33 with the exception of 1-week post injection samples at Weeks 6, 10, 18, 26, 34, week 37(4-week post injection sample) and Week 41
- o. Long-term follow up PK samples: PK sampling during follow up will occur at, Week 53, 65, 77, and 89.
- p. Additional testing is required for participants who have a reactive or positive HIV test after enrolment. Stored plasma from the visit previous to the positive test should be tested for HIV using the 4th generation HIV test to best estimate time of infection. HIV acquisition must be confirmed by either western blot, HIV ½ Multispot or the Geenius HIV Confirmation ½ Assay, and HIV RNA.
- q. Visit may occur in a window ± 3 Days

Table 2 SCHEDULE OF INTENSIVE ORAL PK APPROXIMATELY 16 PARTICIPANTS) ^{a,b}

	Day 25	Day 26	Day 27							Day 28	
	Check-in	Oral dose administered (e.g. 8AM)	Prior to oral dose (e.g. 7:55AM)	Oral dose administered (e.g. 8AM)	1-hour post dose (e.g. 9AM)	2-hour post dose (e.g. 10AM)	3-hour post dose (e.g. 11AM)	4-hour post dose (e.g. 12AM)	8-hour post dose (e.g. 4PM)	24-hour post dose (e.g. 8AM)	Oral dose administered (e.g. after 8 AM)
Plasma for CAB concentration			X		X	X	X	X	X	X	

- a. PK sampling may occur ± 15 min
- b. Central lab tests for the intensive oral PK subjects refer to [Table 1](#).

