7.6. Treatment Compliance

- When participants are dosed at the site, they will receive study treatment directly from the investigator or designee, under medical supervision. The date and time of each dose administered in the clinic will be recorded in the source documents. The dose of study treatment and study participant identification will be confirmed at the time of dosing by a member of the study site staff other than the person administering the study treatment.
- During the oral dosing phase, compliance will be assessed through querying the participant during the site visits and documented in the source documents and CRF. A record of the number of CAB tablets dispensed to and taken by each participant must be maintained and reconciled with study treatment and compliance records. Treatment start and stop dates, including dates for treatment delays and/or dose reductions will also be recorded in the CRF.
- CAB LA 600 mg at weeks 5, 9 and every 8 weeks up to 33 weeks will be intramuscularly administered to participants at the site. Administration will be documented in the source documents and reported in the CRF.

Note:

- CAB LA dosing is expected to occur in a window ± 3 Days

- CAB LA dosing may occur without consultation from the medical monitor if performed within this dosing window.

Any request for dosing to occur outside of the dose week must be discussed and agreed with the medical monitor prior to dosing. In the event of a late dose, a revised dosing schedule for subsequent dosing may be required and will be communicated to the site staff at the time of approval for continued dosing.

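### SAP 10.4.2.1 does not place every adverse event in exactly one treatment state: for participants who complete injections, the on-CAB LA and post-treatment states meet only if the Week 41 visit falls exactly 56 days after the last injection

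*SAP*

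**What the plan says.** SAP 10.4.2.1 assigns AEs to treatment states by start date. The on-CAB LA row has two end points:

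- In general: "Date of First CAB LA Injection ≤ AE Start Date ≤ Date of Week 41 Visit".
- For participants who withdraw from injections: "Date of First CAB LA Injection ≤ AE Start Date ≤ Date of Last CAB LA Injection + 8 Weeks".

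The post-treatment row has one rule for everyone: "AE Start Date > Date of Last CAB LA Injection + 8 weeks".

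SAP 10.4.1 defines study phases on a different basis. The injection phase runs up to "8 weeks after Last CAB LA Injection", and the follow-up phase is everything later. It has no Week 41 visit rule. The primary safety window in SAP 7.1 and Protocol 10.3.1.1 also closes eight weeks after the last injection.

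Both dates that set the boundary can move. The schedule of activities states "Visit may occur in a window ± 3 Days", and Protocol 7.6 states "CAB LA dosing is expected to occur in a window ± 3 Days". Protocol 7.6 also allows dosing outside that window with the medical monitor's agreement.

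For participants who withdraw during the oral phase, SAP 10.4.2.1 closes the oral state at "Withdrawal date + 7 days". SAP 10.4.1 and 8.2 use the date of the last study visit. The SAP file holds two versions of the plan, and the state table reads the same in both.

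**The concern.** A classification rule for AEs should give each event one state. For participants who complete injections, one boundary is an observed visit date and the other is calculated from an injection date, and nothing forces them to agree. The clause for withdrawals in the same row does not have this problem, and the SAP gives no reason for treating completers differently.

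Protocol 10.3.1.1.2 asks for treatment-emergent AE summaries for LA dosing, for oral dosing and for the two combined. The SAP's only AE-specific on-treatment definitions are in 10.4.2.1, so a programmer could reasonably derive treatment emergence from them. Events near the boundary could then be left unclassified or carry two labels.

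**Working it through.** **Inputs**

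- The schedule of activities gives Week 5 = Day 35 and Week 6 = Day 42, so Week *n* = Day 7*n*.
- Planned injection 5 is at Week 33 = Day 231. The planned Week 41 visit is on Day 287.
- Eight weeks = 56 days.
- Visit window ±3 days (schedule of activities); injection window ±3 days (Protocol 7.6).
- Nominal injection phase: (41 − 5) × 7 = 252 days.

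**Rule.** Let I be the date of the last injection and V the date of the Week 41 visit. For a completer, the on-CAB LA state includes days up to V, and post-treatment starts on day I + 57. Let D = V − (I + 56).

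- D = 0: the states meet.
- D < 0: |D| days belong to neither state.
- D > 0: D days belong to both.

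**Nominal schedule.** 231 + 56 = 287, so D = 0. The mismatch comes entirely from visit timing.

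**Within the windows.** The documents do not say what the Week 41 window is measured from, so I took two assumptions.

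| Assumption | D | Date combinations | Gap | Overlap | Meet | Largest mismatch | Share of 252 days |
|---|---|---|---|---|---|---|---|
| Week 41 visit within ±3 days of last injection + 56 | −3 to +3 | 7 | 3 | 3 | 1 | 3 days | 3/252 = 1.2% |
| Injection 5 and Week 41 visit each within ±3 days of the Day 1 schedule | −6 to +6 | 49 | 21 | 21 | 7 | 6 days | 6/252 = 2.4% |

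The counts are of possible date combinations, not probabilities.

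Example of the largest gap: injection 5 on Day 234 and the visit on Day 284. The on-CAB LA state ends on Day 284 and post-treatment starts on Day 291 (234 + 57), so Days 285 to 290 have no state. Example of the largest overlap: injection 5 on Day 228 and the visit on Day 290. Post-treatment starts on Day 285 (228 + 57), so Days 285 to 290 are in both states.

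**Outside the windows.** A later visit makes the overlap longer. With no Week 41 visit, V does not exist, and a participant who had all five injections has no on-CAB LA end date unless counted as withdrawn.

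**Withdrawal clause.** The on-CAB LA state ends at I + 56 and post-treatment starts at I + 57, so there is no gap or overlap. Applying this clause to every injected participant gives the same result for completers.

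**Oral-phase withdrawals.** Post-treatment is defined only from an injection date. An AE starting after withdrawal + 7 days therefore has no state, although under 10.4.1 it is still in the oral phase if it starts on or before the last study visit.

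**The case against.** The strongest reply is that the planned AE tables do not use these states. SAP 7.1.2 tabulates AEs by study phase, SAP 7.1 sets the primary safety analysis in the injection phase, and the phases in 10.4.1 meet exactly. None of the AE tables in SAP Appendix 14 names a treatment state. This stands, and it limits the point.

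A reader might infer that AE counts in the primary injection window will lose or double-count events. The documents do not support that. The primary tables follow the phases, and SAP 7.1 counts each participant once per category. Even if the states were used, an AE in an overlap would count once as on-treatment and again under post-treatment, not twice within the on-treatment column.

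A reader might also take the oral cut-off as the same defect. It is not. It is a difference between two tables, and it creates no overlap between adjoining states. SAP 8.2 already settles the oral analysis by using the last study visit. Participants who stop in the oral phase also leave the study (Protocol 8.1), so few later AEs would be recorded.

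Finally, 6 days should not be quoted alone. Protocol 5.1 times the start of follow-up visits from the last injection, which favours the 3-day bound without settling the anchor.

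What the reply does not remove is that the rule in 10.4.2.1, as written, fails to classify some start days uniquely.

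**Conclusion.** The point holds as a small defect in a stated rule. For completers, the on-CAB LA and post-treatment states in SAP 10.4.2.1 leave a gap or overlap whenever the Week 41 visit is not exactly 56 days after the last injection. Inside the windows the maximum is 3 or 6 days, depending on an anchor that the documents leave open. The rule also disagrees with its own withdrawal clause, with 10.4.1 and with the primary safety window.

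The consequence is confined to AE flags, or to the treatment-emergent summaries in Protocol 10.3.1.1.2, if these are derived from the states. The interval is short, so few events are expected. The oral-withdrawal cut-off is a separate inconsistency of lesser weight.

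**What to change.** In SAP 10.4.2.1, end the on-CAB LA state at last injection + 8 weeks for every injected participant and drop the Week 41 visit date. The states then meet exactly, agree with 10.4.1 and the primary safety window, and also cover a completer who misses Week 41. This costs one line and needs no new data.

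Separately, reconcile the analysis cut-off for oral-phase withdrawals so that 10.4.2.1, 10.4.1 and 8.2 use one rule, and state how an AE after that cut-off is classified. This costs a second line.
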